The proposed study is designed to tailor SPEAK! to the unique needs of people with symptoms of SCD/MCI and gather preliminary data on its feasibility and impact in that population. Despite our extremely encouraging experience to date recruiting older adults for SPEAK! (many of whom have contacted us with little or no prior outreach), an important goal of the R21 will be to determine whether we are able to recruit and retain older adults with symptoms of SCD/MCI as well as their ELL conversation partners at a rate sufficient to ensure accrual goals for the subsequent R01-funded randomized trial. We also will tailor current SPEAK! orientation and session-support materials to address the unique consent and informational needs of people with symptoms of SCD/MCI, and we will gather preliminary data on satisfaction with the SPEAK! experience and its impact on participants' mental health and functioning. The study will provide vital data for the submission of a competitive application for a larger randomized trial evaluating the intervention's impact on SCD/MCI patients' mental health (e.g., depression, loneliness, and sense of purpose) and cognitive functioning. Consistent with the NIA Stage Model for Behavioral Intervention Development, the current study will include elements of Stage 0 (intervention generation, refinement, modification, and pilot testing) and Stages 1-2 (efficacy testing with various levels of control). Specifically, the study will include a mixed-methods user-centered design

process (Aim 1, NIA Stage 0) followed by a randomized waitlist-controlled trial with an 8-week follow-up (Aims 2 and 3, NIA Stages 1-2). The study's specific aims are:

Aim 1: Conduct a user-centered design process to refine the SPEAK! training protocols for older adults with symptoms of SCD/MCI and ELLs, and the materials that will support productive, engaging English conversation practice.

Aim 2: Conduct a randomized, wait-list controlled trial of 8 weeks of SPEAK! participation, using a variety of recruitment sources, in order to evaluate our capacity to recruit, implement the intervention, and retain older adults with symptoms of SCD/MCI in sufficient numbers for a subsequent randomized-controlled trial evaluating the intervention's impact on participants' psychological well-being, mood, and cognitive functioning.

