Overview of the study design. Prior to the waitlist-controlled trial, we will conduct a qualitative, user-centered design process with up to 10 pairs of older adults with symptoms of SCD/MCI and ELLs to iteratively refine the training protocols and the materials that will support productive, engaging conversations. We then will conduct a mixed-methods pilot randomized trial with a waitlist control group in which 44 pairs of older adults with symptoms of SCD/MCI and ELLs will be recruited from a variety of sources. Pairs will participate in webcam conversations supported by research staff for 8 weeks, using materials designed to promote positive and effective conversation sessions. Data will be collected from older adults with symptoms of SCD/MCI and ELLs via observations of videoconference sessions, qualitative semi-structured interviews, and quantitative surveys at baseline and the 8-week follow-up. The primary goal of the randomized pilot study will be to evaluate our capacity to recruit pairs, implement the intervention, and retain participants with symptoms of SCD/MCI in sufficient numbers for a subsequent trial evaluating the intervention's impact on participants' psychological well-being, mood, and cognitive functioning. We also will use mixed methods to evaluate the communication process between older adults with symptoms of SCD/MCI and ELLs including factors that contribute to satisfaction of both parties, engagement in sessions, contributors to dissatisfaction or dropout, and perceptions among older adults with symptoms of SCD/MCI of being appreciated and effective. Finally, using data from the waitlist-controlled trial, we will estimate variances for key outcome variables for planning the subsequent clinical trial, and we will conduct exploratory analyses of intervention-control differences in participants' perceptions of their wellbeing, mood, and cognitive functioning.

Sequence of the investigation. Months 1-6 will be devoted to developing protocols and materials for screening/surveys, recruitment, training, and supervision of sessions. In Months 7-11 we will conduct a user-centered design process (Aim 1) and refine protocols and materials in preparation for the trial. Months 12-17 will be devoted to enrolling 44 pairs of older adults with symptoms of SCD/MCI and their ELL partners for the pilot trial. Older adults' cognitive functioning,

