sense of well-being, and other key variables will be measured using validated scales at baseline and the 8-week follow-up. Data collection will be completed in month 20, waitlist control participants will complete the intervention in month 23, and months 23-24 will be devoted to statistical analysis, presentations, and the submission of an application for a larger, definitive randomized trial focusing on measures of cognitive functioning, well-being, depressive symptoms, and physical health outcomes.

Eligibility and screening of older adults with symptoms of SCD/MCI. To be eligible, older adults with symptoms of SCD/MCI must: be 55+ years of age, fluent speakers of English of any race/ethnicity, and be able to participate in a videoconference via a smartphone, tablet, laptop, or desktop computer in their home or referring organization using a widely-accessible, no cost videoconferencing platform. Participants will be ineligible if they have a history of stroke or traumatic brain injury, bipolar disorder, schizophrenia, or current alcohol or drug abuse/dependence, that would affect their ability to participate in the study. Our primary source of recruits will be the Michigan Alzheimer's Disease Core Center (MADCC) registries which include detailed information about individuals who have indicated a willingness to be contacted regarding studies and have undergone detailed neuropsychologic evaluations. [name] (Co-I) is the Clinical Core Leader for the MADCC and [name] (Co-I) is the MADCC Director for Outreach and Recruitment. More than 100 MADCC registry participants have been identified with MCI and this number is expected to increase. Additional participants will be identified via outreach and referrals from specialty clinics including the UM Cognitive Disorders Clinic, two area community senior centers, as well as Michigan Chapters of the national Alzheimer's Association (see letters of support).

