Online sessions. We will use a standard videoconferencing platform (e.g., "BlueJeans") or the SPEAK! platform for the study. While specially-customized videoconferencing software may be useful, we believe that at this stage of the research it would be wiser to invest resources in first understanding the types of customization that would be beneficial. Both older adults with symptoms of SCD/MCI and ELLs will be sent reminders prior to each session via a telephone call, email, or text message according to their preference. Videoconferences will be facilitated by study staff who will introduce each session, assist with technical issues, and ensure that both parties have their materials and are comfortable. Older adults and learners will be provided with a suggested session outline. More detailed information will be provided in a variety of formats including a comprehensive manual, flashcards, and lists of common phrases to ensure that conversations do not stall. Our expectation based on initial experience with older adults who do not have symptoms of SCD/MCI is that pairs will meet online for a one-hour session once a week for a total of 8 weeks. Meta-analyses of factors determining the impact of volunteering or psychological interventions indicate that effects are not sensitive to the number or duration of sessions. However, we will specifically inquire about the length and frequency of sessions during follow-up surveys and qualitative interviews with participants for Aim 1. Based on that feedback and

more detailed input from experts in gerontologic mental health, the frequency and duration of sessions may be modified.

While we fully expect that conversations will be a positive and productive experience for the older adult with symptoms of SCD/MCI and ELL, training materials will include a discussion of topics that both parties should avoid. These will include financial problems, medical problems, or potentially contentious issues such as political or religious differences. We will make special emphasis regarding types of comments that would be considered inappropriate, even as “jokes.” We will inquire about questions and comments that would be considered too sensitive during the Aim 1 development interviews. Pairs will be instructed regarding the types of information that they should never share, such as financial data, and we will emphasize the importance of being available at scheduled times and communicating in advance if availability changes.

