Aim 2-3 waitlist controlled trial. While our primary scientific goal is not to evaluate intervention-control differences in outcomes, we will include a waitlist control group in order to get an unbiased estimate of recruitment rates for that subsequent randomized clinical trial. We will generate a randomization sequence and randomization envelopes to assign 44 older adults to the intervention or waitlist control group (1:1 ratio). Randomization will be conducted after older adults with symptoms of SCD/MCI complete their baseline survey. Older adults with symptoms of SCD/MCI assigned to the intervention will be matched with an ELL for 8 weeks of hourly SPEAK! sessions with orientation and materials refined as part of Aim 1. Older adults with symptoms of SCD/MCI assigned to the waitlist control will be matched with an ELL after completing their 8-week follow-up survey, at which time the pair will complete the 8-week intervention.

Quantitative measures for Aims 2-3. Older adult with symptoms of SCD/MCI surveys. Sociodemographic characteristics of older adults with symptoms of SCD/MCI will be measured using standard items to evaluate the generalizability of the study findings and possible moderators of intervention effects. General health status will be measured at baseline using standardized items to identify common chronic diseases. At baseline and follow-up, older adults with symptoms of SCD/MCI will complete the Psychological Well-Being Scale (PWB), a validated measure shown to be sensitive to intervention effects and with subscales measuring respondents’ sense of autonomy, environmental mastery, personal growth, positive relations with others, life purpose, and self-acceptance. The PWB will be supplemented with measures

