Additional analysis for Aims 2-3. Older adults with symptoms of SCD/MCI will be asked to consent to a brief screening survey, and initial analyses will focus on the sociodemographic, health, and mental health characteristics of potential participants who do versus do not enroll, and reasons for non-participation. Recruitment rates will be tracked overall as well as by gender, age, race/ethnicity, and educational attainment. Among enrollees, we will calculate descriptive statistics of the proportion of older adults with symptoms of SCD/MCI who choose to discontinue participation, as well as baseline predictors of dropout and session completion, with a particular emphasis on baseline measures of cognitive functioning, and psychological indicators such as PWB and depressive symptoms. While these will be quantitative analyses, results will not include statistical inference (i.e., “p-values”). **For Aim 3.** We will examine correlations between measures of (a) intervention satisfaction and the number of missed sessions, and (b) baseline measures of characteristics of older adults with symptoms of SCD/MCI including measures of cognitive functioning and PWB. Examination of intervention/control differences in PWB will be purely exploratory and used to generate hypotheses and strategies for modifying the intervention to make it more impactful. Change scores for continuous outcomes (e.g., PWB) will be computed, and differences across randomization groups will be compared using the Wilcoxon rank sum test.

In a purely exploratory mode, we will examine differences in outcomes between intervention and control groups, controlling for any baseline differences in group characteristics. Older adults who drop out of the program or who complete less than the expected number of sessions but complete outcome surveys will be included in outcome analyses. We also will conduct 'completer' analyses including only intervention-group older adults who complete 8 out of the 12 planned sessions (or the equivalent out of 8 planned sessions). Whenever possible, we will create graphical displays comparing pre-post changes in outcomes across groups to make the findings as interpretable as possible for various audiences.

IV. Potential Risks, Minimizing Risks, and Potential Benefits

Protection of Human Subjects

Human Subjects Involvement and Characteristics

1. Risk to Subjects

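### Does a completer cut written for 12 planned sessions undermine the analysis of a trial that describes 8?

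*Combined protocol and SAP*

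**What the plan says.** Section III (Additional analysis for Aims 2-3) describes two kinds of outcome analysis. The first compares intervention and control groups and keeps older adults who drop out or attend fewer sessions than expected, provided they complete the outcome surveys. The second is an added completer analysis, restricted to "only intervention-group older adults who complete 8 out of the 12 planned sessions (or the equivalent out of 8 planned sessions"). No whole number is given for the 8-session case and no comparator is named. The paragraph opens by calling these comparisons purely exploratory.

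Elsewhere the schedule is stated as follows:

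- Specific Aims, Aim 2: a "trial of 8 weeks of SPEAK! participation".
- Section II, Online sessions: the expectation is that "pairs will meet online for a one-hour session once a week for a total of 8 weeks". After Aim 1 feedback and expert input, "the frequency and duration of sessions may be modified".
- Section III, Aim 2-3 waitlist controlled trial: intervention adults are "matched with an ELL for 8 weeks of hourly SPEAK! sessions". Waitlist adults get a partner only after their own follow-up survey.
- Section II, Overview of the study design: "quantitative surveys at baseline and the 8-week follow-up".
- Section IV, Potential Benefits: the learner's certificate needs 6 of 8 sessions.

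Section III (Primary outcome and sample size) makes recruitment the criterion for the pilot and says the trial is not meant to estimate effect sizes.

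**The concern.** The figure of 12 planned sessions appears once, in the definition of an analysis set, and conflicts with every other description of the schedule. It reads like a remnant of another design. The parenthesis converts the rule to 8 sessions, but the conversion does not give a whole number, so two analysts could follow the text faithfully and form different completer sets. If the choice were made after outcome data were seen, it could be steered by the results.

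The selection also applies to one arm only. Waitlist adults have no sessions before their follow-up survey, so they cannot be selected on attendance in the same way. Setting intervention completers against all waitlist adults would therefore condition on behaviour after randomisation in one arm. Adjusting for baseline differences does not restore the randomised comparison, and the plan does not say so.

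At stake would be who counts as a completer, and whether a reader might take the completer result for a randomised one.

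**Working it through.** **Inputs from the documents.** Cut: 8 of 12. Alternative planned count: 8. Randomised: 44 older adults, 1:1, so 22 in the intervention arm (Section III, Aim 2-3 waitlist controlled trial).

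**Inputs assumed, because the documents give none.** All 22 are surveyed; mean attendance is 0.7 to 0.8; within-person correlation of attendance is 0.3, with 0 and 0.5 as alternatives.

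**Step 1: the proportion and its conversion.** 8/12 = 66.7%. Applied to 8 sessions: 8 × 8/12 = 5.33. The candidates are 5/8 = 62.5%, which is 4.2 points below the target, and 6/8 = 75%, which is 8.3 points above it. Rounding to the nearest whole number gives 5; reading the rule as a minimum of two-thirds gives 6. Both readings are defensible. The learner's certificate uses 6 of 8, but for a different person and purpose, so it does not decide the matter.

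**Step 2: how many people the choice moves.** Expected completers = 22 × P(sessions attended ≥ cut), with sessions attended following a beta-binomial distribution. At correlation 0.3:

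| Cut | Mean attendance 0.7 | Mean attendance 0.8 |
|---|---|---|
| 5 of 8 | 22 × 0.705 = 15.5 | 22 × 0.825 = 18.1 |
| 6 of 8 | 22 × 0.592 = 13.0 | 22 × 0.739 = 16.3 |
| 8 of 12 | 22 × 0.653 = 14.4 | 22 × 0.790 = 17.4 |

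The people who change status are those attending exactly 5 of 8. From unrounded probabilities:

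| Correlation | Mean attendance 0.7 | Mean attendance 0.8 |
|---|---|---|
| 0 | 5.6 | 3.2 |
| 0.3 | 2.5 | 1.9 |
| 0.5 | 1.5 | 1.2 |

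In the first table the 8-of-12 count lies between the two 8-session cuts and is slightly nearer to 5. That is no basis for insisting on either.

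**Step 3: does the 12 reach anything else?**

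- *Recruitment criterion.* Fewer than 35 pairs in 6 months is the warning level. The Poisson probability of fewer than 35 is 0.072 at a mean of 44 and 0.079 at a mean of 262/6 = 43.67, consistent with the stated P<.10. Session counts do not enter.
- *Main exploratory comparison.* Partial attenders with outcome surveys stay in, so no attendance cut applies.
- *Correlation of satisfaction with missed sessions.* Missed = planned − attended. With one planned count for everyone, changing 8 to 12 adds 4 to each person's value, and a correlation is unchanged by adding a constant.
- *Engagement as a percentage.* Six attended is 75% of 8 and 50% of 12, so the denominator would matter. But the stated schedule gives 8, and nothing in the protocol uses 12 for this purpose.

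**Step 4: can the two counts coexist?** One session a week for 8 weeks gives 8 sessions before the week-8 survey. Twelve in 8 weeks would be 12/8 = 1.5 a week, which would need the change of frequency that the Online sessions text allows. The dual wording is therefore consistent with a rule drafted before the schedule was fixed.

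**Step 5: size of the selection effect.** The documents give no relation between attendance and change in outcome, so neither the direction nor the size of any bias in a completer comparison can be computed.

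**The case for a change.** The strongest case for a change is that it costs almost nothing. About two sentences would fix a whole-number cut before outcome data are seen, name the comparator and label the result as non-randomised. Engagement is one of the pilot's key processes, so a single planned session count is useful. Calling an analysis exploratory also tells a reader that it is tentative; it does not say that this contrast, unlike the main one, has lost randomisation.

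Much of that stands as good practice. The text leaves 5 or 6 open, and a completer-versus-waitlist result, if produced, should be reported as non-randomised. But these are details that a competent analyst supplies when writing the analysis code and the report. The plan already separates the completer analysis from the one that keeps partial attenders, gives it no decision role and disclaims effect estimation. The comparator is unstated, so the loss of randomisation depends on how the analysis is carried out and is not an error already in the plan. The 12 causes trouble only if carried into the final analysis of an 8-session programme, and the parenthesis provides for that case.

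**Conclusion.** The observation is accurate, but it does not call for a change to the plan. The plan gives a two-thirds rule for one possible schedule and says to use its equivalent for the other. What is missing is a rounding convention and a reporting label, both in a supplementary analysis. Under assumed attendance of 0.7 to 0.8, the rounding choice moves about 2 of 22 people at correlation 0.3, and from about 1 (correlation 0.5) to about 6 (independence) over the range examined. Those counts rest on attendance assumptions that the documents do not supply. The recruitment criterion, the main exploratory comparison and the missed-session correlation are unaffected whichever number is used. Following the plan as written, with the cut settled before outcomes are examined and the completer result described for what it is, leads to no wrong conclusion about the pilot's aims.
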